## Evaluation of novel cone-beam CT for guidance and adaptation of precision radiotherapy

Summary of Changes from Previous Version:

Version	Affected Section(s)	Summary of Revisions Made	Rationale
1.0		Initial Release	
2.0	Protocol signature page	Corrected version date	Administrative
	Synopsis	Fixed typographical error	

## Abbreviations

AE	Adverse event
API	Application programming interface
CBCT	Cone beam CT
CIP	Clinical investigation plan
CNR	Contrast-to-noise ratio
CT	Computerized tomography
CTCAE	Common Terminology Criteria for Adverse Events
DEBH	Deep expiration breath hold
DIBH	Deep inspiration breath hold
EC	Ethical Committee
HR	Human resources
HU	Hounsfield Unit
IGRT	Image-guided radiation therapy
IRB	Institutional Review Board
ISO	International Organization for Standardization
NS	Nova Scotia
NSHA	Nova Scotia Health Authority
QE2	Queen Elizabeth II
REB	Research ethics board
RT	Radiation therapy
SABR	Stereotactic Ablative Radiation Therapy
SAE	Serious adverse event

## SYNOPSIS

Title:	Evaluation of novel cone-beam CT for guidance and adaptation of precision radiotherapy
Study Description:	This is a feasibility study investigating the image quality of a new, high-performance cone beam CT (CBCT) used for on-couch imaging during radiotherapy treatments.
Objectives:	
Primary Objective: Compare – quantitatively and qualitatively – CBCT images acquired by the high-performance system to both CBCT images acquired using a standard system and to fan beam CT images acquired for radiotherapy dosimetry planning.
 
Secondary Objectives: (1) Compare the radiation dosimetry calculated from the high-performance CBCT images to that calculated from both standard CBCT images and fan beam CT images. (2) Compare the patient experience between faster acquisition of the high-performance CBCT, which enables acquisition with a single breath hold, versus slower acquisition of a standard CBCT requiring potentially multiple breath holds.

Metrics:	
Images will be evaluated quantitatively by calculating contrast-to-noise ratio (CNR), resolution, Hounsfield Unit (HU) accuracy and artifact reduction.
 
Radiation oncologists and radiation therapists will compare image sets and rank them according to usefulness for anatomical structure delineation and patient positioning, respectively.
 
Anatomical structures from a subject's dosimetry plan will be deformably registered from the planning fan beam CT to the CBCTs acquired for that subject. Dosimetry will be calculated from all three registered image sets and dose-volume histograms will be compared.
 
Subjects will complete a questionnaire evaluating their experience of the two different CBCT acquisition processes.

Study Population:	Adult cancer patients undergoing radiotherapy where a breath hold is required for imaging and/or treatment delivery.
Phase:	Feasibility study

Description of Sites/Facilities Enrolling Participants:	This is a single-site study that will take place at the QE2 location of Nova Scotia Health.
Description of Study Intervention:	Two additional CBCT images will be acquired, one with a breath hold, the other with free breathing. Participation in the protocol will not alter a patient's cancer treatment.
Study Duration:	One year
Participant Duration:	1-4 weeks

# 1 INTRODUCTION

## 1.1 Study Background and Rationale

This study focuses on potential benefits of a high-performance cone beam CT (CBCT) image guidance system for improved precision in the delivery of radiotherapy. This imaging system is a component of a forthcoming radiation therapy (RT) treatment platform, called Ethos (Varian Medical Systems), to be installed and commissioned clinically at the Nova Scotia Health QE2 site in Q1 2022.

Radiation therapy is used in the treatment of approximately 50-60% of all cancer patients. Image guided radiation therapy (IGRT) is now a standard of care for external beam radiotherapy. During an IGRT treatment session, a CBCT imaging system built into the treatment unit allows 3D visualization of the patient's anatomy immediately prior to, and, if required, at several time points during the delivery of radiation. The CBCT image data are used by the treatment team to carefully align the patient to their previously acquired treatment planning CT. Verification of the patient position and alignment with the treatment planning images increases the precision of radiation delivery. IGRT is available on all eight treatment units in Nova Scotia and is central to their procedures for delivery of precision RT.

Although IGRT has facilitated breakthroughs in the precision and accuracy of RT over the past two decades, the imaging technology has remained limited in some respects, particularly in the amount of time it takes to acquire a CBCT image. The current acquisition duration of approximately one minute does not allow image guidance in scenarios where high temporal resolution is required. This limitation is most evident in clinical situations where tumours move during treatment delivery, e.g., breast, liver, or lung tumours that move with the patient's respiration. In this scenario, both the CBCT image acquisition and radiation delivery is accomplished at NS Health by the patient performing multiple breath-hold maneuvers in an effort to 'freeze' the motion of the tumour, which may otherwise move by up to 3 cm. Deep Inspiration Breath Hold (DIBH) or Deep Expiration Breath Hold (DEBH) approaches are both used at NS Health, depending on the indication. Because complete acquisition of a CBCT image may require 60 seconds and because many patients who are treated with IGRT have limited ability to maintain DIBH or DEBH for extended periods, up to eight (Boda-Heggemann et al., 2011) separate breath hold maneuvers may be needed to acquire a complete image set.

The multiple-breath-hold CBCT acquisition approach has two key disadvantages. First, the total treatment time is significantly extended, especially if multiple CBCT acquisitions are required (e.g., for pre- and post-alignment of the patient, and particularly for patients with compromised respiratory function, who need time to recover from each breath hold). Longer treatment times impact resources (capital and HR) and are deleterious to the overall patient experience. Second, since each breath hold is not performed identically by the patient (e.g., in terms of breath hold amplitude),

inconsistencies are introduced in the reconstructed image data, resulting in poorer image quality. By forming an image from piecewise sets of projections, one per breath hold, image quality is compromised by motion artifacts (Kashani et al., 2006) due to the variability of the patient's anatomy between projection sets. An example of this from practice, in the context of Stereotactic Ablative Radiation Therapy (SABR) of the liver, is shown in [Figure 1](#).

Figure 1 Status-quo CBCT image used for guidance of Stereotactic Ablative Radiation Therapy (SABR) of the liver. Multiple breath-hold maneuvers necessitated by the acquisition of this dataset causes marked artifacts (white arrows) at the dome of the liver and compromises the accuracy of aligning the anatomy for treatment.

NS Health has been performing breath-hold CBCT guidance for many years for patients with primary or metastatic liver cancer, T1-T2 lung cancer, and left-sided breast cancer and thus the treatment teams are acutely aware of the limitations of the technique.

There exists a compelling need for rapid CBCT image acquisition for guidance of RT. To date, CBCT acquisition within the timeframe of a single breath-hold has been limited to pre-clinical investigations (Arns et al., 2019). The high-performance CBCT system being developed for the Ethos treatment platform will allow image acquisition within approximately six seconds and with increased x-ray efficiency. Most patients can maintain a breath hold for six seconds and so the high performance CBCT system can potentially acquire an image with a single breath hold in a clinical setting. This improvement should result in higher quality intra-treatment imaging and a better patient experience. The x-ray efficiency improvement has the potential to improve image quality or reduce imaging dose to the patient. Improvements in motion artifact suppression algorithms used in the image reconstruction process may even improve quality of images acquired during free breathing, i.e., without a breath hold, which would have a

positive impact for patients who cannot maintain a breath hold due to significantly compromised respiratory function.

As explained in the objectives below, we expect that the Ethos CBCT will introduce previously unrealized image quality and anatomy visualization for on-couch imaging that will improve the precision of treatment delivery. Should this be the case, the improvement in intra treatment image quality will influence clinical practice on multiple fronts. The potential improvements in precision that come from better on-couch imaging may enable hypofractionation of patient treatment, e.g., compression of a 20+ daily fraction treatment course to 5 fractions, because higher fractional doses can be delivered safely. Improvements in visualization of anatomy resulting from increased image quality may enable accurate online adaptation of a patient's treatment plan in the presence of inter-fraction anatomical change. It may also facilitate development of rapid treatment paradigms without the need for a simulation procedure. For example, a patient with spinal cord compression could both have a treatment plan generated from the Ethos CBCT and then receive treatment on the Ethos platform, reducing time to treatment to one hour instead of one day.

With minimal disruption for participating patients, this study will enable a comparison of (i) the patient's treatment planning fan-beam CT and (ii) the patient's status-quo CBCT on an existing treatment unit with (iii) the high-performance CBCT on Ethos. Image quality of the high performance CBCT will thereby be compared to both a best-case standard (fan-beam) and the status-quo for IGRT to isolate and identify improvements. Image quality will be quantified in terms of contrast-to-noise ratio (CNR), resolution, Hounsfield Unit (HU) accuracy and artifact reduction with a focus on anatomy germane to the image guidance task. A qualitative assessment of the different image datasets will also be performed through feedback from multiple observers (radiation oncologists and radiation therapists). Radiation doses to key treatment targets and organs at risk will be calculated from the high performance CBCTs to determine the suitability of the CBCT images for RT dosimetric planning. Patient experience will be evaluated through questionnaires.

Image sets (i) and (ii) are already acquired as part of standard-of-care for radiation treatment. Two additional CBCTs, one with breath hold and the other with free breathing, will be acquired from each subject on the Ethos platform for this study. Radiation treatment planning and delivery will not be altered due to patients' participation in this study. Patients will receive radiotherapy according to current departmental procedures and on the department's existing linear accelerator platforms.

## 1.2 Risk/Benefit Assessment

### Potential risks of this study:

In routine clinical practice, the standard IGRT workflow may involve multiple CBCT acquisitions during each treatment session to ensure proper patient alignment. Patients

enrolled in this study will undergo two additional research CBCTs (high performance CBCTs on Ethos), both of which will be acquired during a single treatment visit. The radiation dose associated with these two additional CBCTs is approximately 1/5000 to 1/1000 of the dose that the patient will be receiving from the radiation therapy itself. To put this additional dose into perspective, it is helpful to understand that in routine radiotherapy there is inherent and acknowledged uncertainty in the delivered radiation dose. This uncertainty can be 3-5% of the prescribed dose. The dose from the two research CBCTs represents just an additional 1/50th of the already existing uncertainty. Thus, for this patient group, there should be no statistically detectable harm from the two additional CBCTs, e.g., with regard to late effects of the additional radiation.

There is also a potential risk for loss of patient privacy associated with the collection of patient data for this study. This risk will be mitigated by collecting only data that are necessary for the analyses specified in this protocol, by linking data to an anonymized research identifier and by storing data in a secure location to which access is controlled and audited.

#### Potential benefits:

This study is being performed to assess the potential advantages of a high-performance CBCT image guidance technology for future patients who will eventually be treated using this platform. The results may influence the development of new workflows that improve precision of RT through image guidance, as well as workflows for dosimetric plan adaptation based on daily CBCT imaging. One of the key potential benefits for future patients resulting from these new workflows may be lower doses to healthy tissues and reduced toxicity from the radiation treatments. The new knowledge acquired in this study will facilitate implementation of Ethos at NS Health (multiple Ethos platforms are anticipated in a new facility slated to open in 2026). The results will also be of great value to the broader radiation oncology community.

There are no direct benefits expected to the subjects participating in the study. The high performance CBCT images acquired for this study will not be used to make clinical decisions. However, due to the anticipated improved image quality of the Ethos-acquired CBCT, the Principal Investigator may make observations that could improve image guidance for the patient on the actual treatment unit. Such observations will be communicated to the patient's treatment team and must be confirmed with standard imaging prior to making any potential changes in the patient's treatment.

#### Assessment of potential risks and benefits:

On balance, given that the dosimetric risks to patients are very low, and there is significant potential benefit to future patients, the benefits of the study outweigh the risks.

## 2 OBJECTIVES AND ENDPOINTS

### 2.1 Study Objectives

The **primary objective** of the study is to compare

- The quality of high-performance Ethos CBCT images (acquired with breath hold and under free breathing) with that of fan-beam CT (CT simulation) acquired with breath hold, where the latter represents a best-case benchmark; and
- The quality of high performance Ethos CBCT images (acquired with breath hold and under free breathing) with that of Truebeam CBCT acquired with breath hold, where the latter represents the status-quo for image guidance.

The **secondary objectives** of the study are:

1. To compare treatment dosimetry calculated on the Ethos CBCT images to that calculated on both the fan-beam CT and the Truebeam CBCT.
2. To compare the patient experience of CBCT image acquisition between the Ethos CBCT and the existing Truebeam CBCT.

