3. Anonymized fan-beam CT images, status-quo CBCT image and Ethos CBCT image data sets (with breath hold and with free breathing) will be presented to multiple observers for qualitative assessment of perceived image quality. Observers will include up to five radiation oncologists and five radiation therapists, who will answer questions on image quality for contouring and image guidance purposes, respectively. Image quality will be scored either as a simple ranking (1 to 3) or using a five-point Likert scale. This review will be done using the MeVis framework (see example, Figure 2) that allows centralized user management and authentication, ensuring controlled access to data with unique login credentials for each individual. In the case of Likert scale ranking, analysis will be performed using a Mann-Whitney test.

[figure not shown]

Figure 2 Example of qualitative image review using the MeVis framework.

4. A patient experience questionnaire will be provided to each subject on the day they undergo CBCT imaging on the Ethos platform. Subjects will be encouraged to fill out the questionnaire on that day. Study coordinators will transcribe subject responses into the study database.

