## 10 STATISTICAL CONSIDERATIONS

### 10.1 Sample Size

The study design does not involve any intervention in the subject's cancer care. The study is being performed to assess the image quality in a new CBCT system.

This study will accrue thirty (30) subjects, which will include:

- A minimum of 7 subjects with liver cancer
- A minimum of 7 subjects with lung cancer
- A minimum of 7 subjects with cancer in the left breast

Subjects with other cancers can be included so long as the patients meet the study's inclusion/exclusion criteria.

Seven subjects in each cohort will provide sufficient image data for a range of subject variation in the same anatomical site.

Data will be collected and analyzed as described in Section 5. Quantitative image quality metrics for the different imaging modalities will be compared using average values and standard deviations. Qualitative evaluations of image quality using a Likert scale will be compared using a Mann-Whitney test. Dosimetry will be compared using average values of metrics derived from dose-volume histograms and standard deviations of those values. Patient experience of the different CBCT acquisitions will be compared qualitatively based on responses to questionnaires.

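### The plan treats fan-beam CT as the benchmark but plans no within-subject difference or interval showing how far Ethos falls short of it and how precisely that is known

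*Combined protocol and SAP*

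**What the plan says.** The two bullets of the primary objective (protocol section 2.1) give the comparators different roles. Fan-beam CT is "acquired with breath hold, where the latter represents a best-case benchmark". TrueBeam CBCT is the comparator "where the latter represents the status-quo for image guidance". Section 1.1 repeats the contrast: Ethos image quality is to be "compared to both a best-case standard (fan-beam) and the status-quo for IGRT to isolate and identify improvements". It adds that doses calculated on the Ethos images will be used to judge whether those images suit dose planning.

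Sections 5.2 and 10.1 contain the whole analysis plan:

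- **Image metrics:** "Quantitative image quality metrics for the different imaging modalities will be compared using average values and standard deviations". Under section 5.2, resolution is assessed by comparing HU profiles and artifacts are judged qualitatively.
- **Dosimetry:** "Dosimetry will be compared using average values of metrics derived from dose-volume histograms and standard deviations of those values".
- **Reader assessment:** "Image quality will be scored either as a simple ranking (1 to 3) or using a five-point Likert scale". A test is named only for the second option: "Qualitative evaluations of image quality using a Likert scale will be compared using a Mann-Whitney test".
- **Sample size:** 30 subjects, with at least 7 each for liver, lung and left breast. The reason given is "Seven subjects in each cohort will provide sufficient image data for a range of subject variation in the same anatomical site".

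Every subject contributes all four image sets: fan-beam, TrueBeam, and Ethos with and without breath hold. The documents state no confidence interval, within-subject difference, margin, significance level, power or unit of analysis for the reader scores.

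**The concern.** Against a status quo, one asks whether the new system is better, and a difference test is a natural tool. Against a best case, a significant difference mostly confirms what was expected, and a non-significant one leaves open whether the gap is small or the data are few. What informs a reader is the estimated shortfall with its uncertainty. The objective's verb is only to compare, so reading the first bullet as a question of closeness is an inference. It is a fair one, given the benchmark label and the stated interest in suitability for planning.

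The plan makes no distinction between the two comparators. For most endpoints it gives a shortfall without its precision. For Likert scores it gives a difference test that also ignores the pairing. At stake is whether the study's main description, how close Ethos comes to planning CT, can be read with a known degree of certainty.

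**Working it through.** **Inputs from the documents:** n = 30 in total, with a minimum of 7 per named site; all modalities imaged in each subject; Mann-Whitney for Likert scores only.

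**Assumptions, because the plan states none:** two-sided 5% level, normal scores, one score per subject per modality, and shortfalls of 0.5 to 1.0 SD. The planned sample size cannot be reproduced, since its justification is qualitative.

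**1. Why separate SDs do not give the precision of the difference.** The variance of the within-subject difference is s₁² + s₂² − 2·r·s₁·s₂, and the plan does not report r. With s₁ = s₂ = 1 the SD of the difference is √(2(1 − r)):

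| r | SD of difference | 95% half-width at n = 30 |
|---|---|---|
| 0 | 1.41 | 0.53 |
| 0.5 | 1.00 | 0.37 |
| 0.8 | 0.63 | 0.24 |

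The same reported averages and SDs are thus compatible with half-widths that differ by more than a factor of two.

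**2. Precision available from a paired analysis.** The half-width is t(0.975, n − 1)/√n, in units of the SD of the paired differences.
- n = 30: 2.045/5.477 = 0.37.
- n = 7: 2.447/2.646 = 0.92.

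**3. How often a real shortfall is non-significant with a correct paired t-test, n = 30** (noncentral t, noncentrality d√n, d in SDs of the paired differences).
- d = 0.5: noncentrality 0.5 × 5.477 = 2.74, power about 75%, missed about 25%.
- d = 0.8: missed about 1%.

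**4. The same with the planned Mann-Whitney test, n = 30** (d in SDs of the scores). The approximate power is Φ(d·√(0.955·n/2) − 1.96), where 0.955 is the test's efficiency under normality.
- d = 0.5: 0.5 × √14.325 = 1.89, power 47%, missed 53%. Simulated five-point scores with within-subject correlation 0 and 0.5 give power 43% and 40%, so 57% and 60% missed.
- d = 0.8: power 86%; simulated 81% and 88%.
- d = 1.0: power 97%; simulated 94% and 99%.

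The SD units in steps 3 and 4 coincide only when r = 0.5. In that case, for d = 0.5, the simulated power on five-point scores is 40% for Mann-Whitney and 65% for the signed-rank test. The difference is the price of ignoring the pairing.

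**5. Reader clustering.** Up to five readers score each image set for each task. If five ratings are pooled as independent, simulated power at 0.5 SD with 30 subjects is 94–99.5%. The false-positive rate, nominally 5%, then ranges from about 1% to 15–17% depending on the correlation structure. The apparent gain therefore comes with an uncontrolled error rate, and it still gives no interval for the shortfall.

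**The case against.** The strongest reply is that this is a descriptive feasibility study. Its quantitative and dosimetric comparisons are never tested, so they produce no p-value to misread. Subtracting the group averages already gives a shortfall estimate. Even the Mann-Whitney test falls away if readers rank instead of scoring on a Likert scale. All of this stands, and it confines the difference-test problem to Likert reader scores. It does not supply the missing precision: step 1 shows that the uncertainty of the paired difference cannot be recovered from separate SDs. A descriptive study is better served by estimates with intervals.

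A reader might infer that the study intends to declare Ethos no different from planning CT on the strength of a non-significant test. The documents do not say so; they leave that reading open without planning it. A reader might also infer that a test in seven subjects will be used to pass each tumour site. No per-site test is specified, and seven is an accrual minimum. Miss rates at n = 7 would therefore describe an analysis the plan does not contain. The half-width of 0.92 SD matters only as a caution about how by-site summaries are presented.

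It would also go too far to say that the plan can tell nothing about closeness. With 30 subjects, large shortfalls in reader scores would usually be detected. Requiring a formal equivalence margin in a study of this size is debatable.

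**Conclusion.** The concern holds in limited form. For the fan-beam comparison the plan yields point differences without their precision. For Likert scores, if used, it yields an unpaired difference test whose non-significance would not show closeness. At n = 30 the exposure lies in moderate shortfalls: about 25% missed at 0.5 SD of the paired differences with a correct paired test, and about 53–60% at 0.5 SD of the scores with Mann-Whitney. These figures rest on the assumptions listed in the working, especially one score per subject per modality; the plan does not state its unit of analysis. Moving to a paired test improves efficiency but does not by itself answer the closeness question.

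**What to change.** In section 10.1:

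1. For each quantitative image metric, dose-volume metric and reader score, report the within-subject Ethos minus fan-beam difference with a 95% CI. Do this separately for the breath-hold and free-breathing Ethos scans.
2. Average reader scores over readers within subject, or otherwise account for reader clustering, and state the unit of analysis.
3. Do the same for Ethos minus TrueBeam, with a paired test in place of Mann-Whitney if a test is wanted.
4. State that a non-significant difference from fan-beam CT will not be reported as comparability. Optionally, allow a claim of comparability only if the CI lies within a margin fixed before the reads.
5. Present any by-site results as imprecise.

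A share-of-gap-closed ratio, (Ethos − TrueBeam)/(fan-beam − TrueBeam), is unstable when the fan-beam to TrueBeam gap is small. It should be left out or labelled exploratory.

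The cost is some SAP wording and a little more analysis, with no added subjects or imaging. The downside is that claims of matching planning CT become harder to make.
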